### **9.3 Demographic and Baseline Characteristics**

Pre-treatment demographics and subject characteristics will be summarized. Descriptive statistics [e.g., number of subjects, mean, standard deviation (SD), median, minimum, and maximum] will be calculated for continuous variables [e.g. age and weight] and frequency counts will be tabulated for categorical demographic variables [e.g. gender, ethnicity, race, underlying malignancy or leukemic disease at transplant, donor type, donor compatibility, HSCT source, grade of aGVHD at onset, grade of aGVHD at baseline]. Time from HSCT to onset of aGVHD and onset of aGVHD to initiation of study drug will be summarized. Involvement of the skin, lower gastrointestinal (GI) tract, and liver will be summarized by the number of subjects with one organ, two organs, or all three organs involved at baseline.

### **9.4 Safety Data Analysis**

#### **9.4.1 Adverse Events and Serious Adverse Events**

All (serious) adverse events in this study will be collected from the time the subject signs the ICF. All (S)AEs will be collected in this study and summarized by treatment, dose, and severity. Numbers and rates of TEAEs and other safety variables will be tabulated by organ system and preferred term.

At each time point, vital signs and safety laboratory parameters will be tabulated. The continuous variables will be summarized by the descriptive statistics – mean, standard deviation, median, minimum and maximum. Additionally, vital signs and laboratory parameters will be assessed for clinically significant abnormalities as well as shifts from baseline.

#### **9.4.2 Survival to Day 180**

The number of subjects alive, deceased, lost to follow-up, or withdrawn from Day 0 (Protocol MSB-GVHD001) to Day 180 (Protocol MSB-GVHD002) will be summarized in a Subject Disposition table. For subjects who died, the time to event will be calculated from date of transplant, date of aGVHD onset, and date of treatment initiation. All other subjects will be censored and survival time will be calculated from the date of transplant, date of aGVHD onset, or date of treatment initiation to the date of last contact.

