### 5.2 Eligibility Criteria

#### 5.2.1 Inclusion Criteria

Subjects are eligible for the study if all of the following criteria are met:

1. Subjects must have participated in Protocol MSB-GVHD001 and have received at least one infusion of remestemcel-L.
2. Subject or subject's authorized representative must provide written informed consent. Assent, if applicable, must also be collected when required by the IRB/EC.
3. Female subjects of childbearing potential ( $\geq 10$  years of age) ([Appendix 7](#)) must use a medically accepted method of contraception and must agree to continue use of this method for the duration of the study and for the follow-up time period. Acceptable methods of contraception include abstinence, barrier method with spermicide, intrauterine device (IUD), or steroidal contraceptive (oral, transdermal, implanted, and injected) in conjunction with a barrier method.
4. The subject must be willing and able to comply with study procedures, remain at the clinic as required during the study protocol, and return to the clinic for the follow-up evaluations as specified in this protocol.

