## 9. STATISTICAL CONSIDERATIONS AND ANALYTICAL PLAN

### 9.1 Statistical Analysis Plan

Since this is an extension trial of MSB-GVHD001, data presented for MSB-GVHD002 will be presented in two ways:

1. For the extension period only. This will include assessments beyond Day 100.
2. For the entire period spanning both MSB-GVHD001 and MSB-GVHD002 trials.  
In particular, this includes time-to-event data (flares and therapy escalation), survival data, incidence of cGVHD, and frequency of flares.

Categorical variables will be summarized using frequencies and percentages. Continuous variables will be summarized using descriptive statistics (n, mean, standard deviation [SD], median, minimum, and maximum). Confidence intervals, if presented, will have a two-sided 95% confidence level. For time-to-event variables, Kaplan-Meier curves will be presented as appropriate.

In general, the baseline value for a variable is defined as the last non-missing observation prior to or equal to the first dose date of study treatment in MSB-GVHD001. Baseline for analyses of the entire period of MSB-GVHD001 and MSB-GVHD002 will be the same as baseline defined for Protocol MSB-GVHD001. The baseline for the extension period beyond Day 100 will be the same values at the end of study/Day 100 for MSB-GVHD001. Data collected at unscheduled time points will not be summarized at the unscheduled time points.

The actual day relative to start of treatment will be determined from the first dose date in Protocol MSB-GVHD001, which will be considered 'Study Day 0'. Study day will be calculated from the first infusion date in Protocol MSB-GVHD001. A detailed statistical analysis plan (SAP) will be finalized prior to the database lock.

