### 9.2 Analysis Population

The analysis population for safety in this study, the Safety Population, will include all subjects who received at least one dose of the study treatment in study MSB-GVHD001 and entered into study MSB-GVHD002. The population to be evaluated for duration of response will include all subjects who participated in Protocol MSB-GVHD001, received the first 8 doses of remestemcel-L as outlined in that protocol, and showed overall response (OR) or very good partial response (VGPR) to remestemcel-L at Day 28.

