## **9.5 Secondary Endpoints Analysis**

### **9.5.1 Assessment of Survival at Day 180**

Survival will be assessed from initial remestemcel-L treatment to the end of study/Day 180. The numbers with percentages for survival, non-survival, or missing, including lost to follow-up, will be summarized at Day 180. For tabulating responders at Day 28 from the MSB-GVHD001 study versus survivors at Day 180 the present study, percentages of survivors and deaths will be based on all subjects, including those with missing survival information for the lost to follow-up or withdrawn subjects. The association between Day 28 OR and survival at Day 180, and between Day 28 VGPR and survival at Day 180, will be tested for statistical significance. First, the associations will be tested using a Cochran–Mantel–Haenszel (CMH) test, stratifying by baseline aGVHD grade. Day 180 survival Kaplan-Meier curves will be plotted by Day 28 responder and non-responder groups, and differences between these groups will be tested for any statistically significant difference using the log-rank test. The odds ratio for survival at Day 180, given responder status at Day 28, will be presented and tested for statistical significance (whether statistically significantly greater than 1).

[REDACTED]

[REDACTED]

[REDACTED]

[REDACTED]

[REDACTED]

[REDACTED]

[REDACTED]

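### Survival timed from transplant and from aGVHD onset counts time in which no analysed child could have died, so ordinary Kaplan-Meier estimates from those two origins are biased upward

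*Combined protocol and SAP*

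**What the plan says.** Section 9.4.2 sets three time origins. For deaths: "For subjects who died, the time to event will be calculated from date of transplant, date of aGVHD onset, and date of treatment initiation". For everyone else, who is censored at last contact: "survival time will be calculated from the date of transplant, date of aGVHD onset, or date of treatment initiation".

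Entry depends on treatment. Section 5.2.1 states: "Subjects must have participated in Protocol MSB-GVHD001 and have received at least one infusion of remestemcel-L". Section 9.2 defines the Safety Population as all "subjects who received at least one dose of the study treatment in study MSB-GVHD001 and entered into study MSB-GVHD002".

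Day 0 is the first infusion (Section 9.1: "Study day will be calculated from the first infusion date in Protocol MSB-GVHD001"). On method, Section 9.1 says: "For time-to-event variables, Kaplan-Meier curves will be presented as appropriate". It lists survival among the data to be presented over the whole period of both studies. Neither section mentions delayed entry, left truncation or conditioning on survival to infusion.

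The lags appear only as baseline descriptors in Section 9.3: "Time from HSCT to onset of aGVHD and onset of aGVHD to initiation of study drug will be summarized".

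The secondary survival analysis uses one origin (Section 9.5.1): "Survival will be assessed from initial remestemcel-L treatment to the end of study/Day 180".

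**The concern.** A child reaches this study only after transplant, onset of aGVHD, failure of steroids and a first infusion. Children who died before infusion are absent by selection. A Kaplan-Meier curve started at transplant or onset places every analysed child in the risk set from that earlier date, although no death among them could occur before infusion. The denominators are too large over that stretch, the estimated hazard is too low and the survival curve too high. The later a child was infused, the larger the effect, whatever the product does.

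Evaluation stops at Day 180 from first infusion (Section 6.2). A given day after transplant therefore falls at a different point after infusion for each child, so these curves mix outcome with the timing of referral.

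At stake is how two supplementary survival summaries in a single-arm study are read. Without a label, a transplant-origin curve will be taken as the survival of transplanted children, and an onset-origin curve as that of children with aGVHD.

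**Working it through.** The plan states no survival target, event count or sample size for this analysis, so there is no figure of its own to reproduce. The direction follows from the design. The size has to be illustrated.

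**Inputs.** From the documents: the three origins (9.4.2), the infusion requirement (5.2.1, 9.2), Day 0 at first infusion (9.1) and evaluation to 180 days after it (6.2). Assumed: a constant hazard λ after infusion; 180-day survival from infusion S of 60%, 70% or 80%; and a transplant-to-infusion lag uniform on 20 to 60 days or on 30 to 120 days.

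**Formulas.** λ = −ln(S)/180. With a lag uniform on (a, b), nobody is censored before day a + 180, which is after day 180 from transplant. The ordinary Kaplan-Meier value at day 180 after transplant is then the average of exp(−λ(180 − lag)):

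ordinary = S × [exp(λb) − exp(λa)] / [λ(b − a)].

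With delayed entry nobody is at risk before day a, so the target is

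delayed entry = exp(−λ(180 − a)).

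**Worked case, S = 70%, lag 30 to 120 days.** λ = 0.3567/180 = 0.001982. Ordinary = 0.70 × (1.2684 − 1.0613)/(0.001982 × 90) = 81.3%. Delayed entry = exp(−0.001982 × 150) = 74.3%. Excess 7.0 points.

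| S from infusion | Lag (days) | Ordinary | Delayed entry | Excess (points) |
|---|---|---|---|---|
| 60% | 20–60 | 67.3% | 63.5% | 3.7 |
| 70% | 20–60 | 75.8% | 72.8% | 3.0 |
| 80% | 20–60 | 84.1% | 82.0% | 2.1 |
| 60% | 30–120 | 74.4% | 65.3% | 9.1 |
| 70% | 30–120 | 81.3% | 74.3% | 7.0 |
| 80% | 30–120 | 87.8% | 83.0% | 4.8 |

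A simulation of 20,000 children per setting gave the same pattern. The excess was 2.1 to 4.1 points for the shorter lags and 5.3 to 9.5 for the longer; the differences from the table are simulation noise. Hence the rounded ranges of 2 to 4 and 5 to 10 points.

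**Second check, usable for either origin.** Let the same constant hazard run from the early origin and let every child be infused after a fixed lag L. True 180-day survival is exp(−180λ). The estimate among children who reach infusion is exp(−(180 − L)λ), too high by the factor exp(λL). To set λ only, take the one-year survival of 5% to 30% quoted in Section 1.2, so λ = −ln(one-year survival)/365.

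| Lag L (days) | Excess if one-year survival is 5% (true 22.8%) | Excess if 30% (true 55.2%) |
|---|---|---|
| 7 | 1.3 points | 1.3 points |
| 14 | 2.8 | 2.6 |
| 30 | 6.4 | 5.7 |
| 60 | 14.5 | 12.1 |

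This table measures against all children from the origin; the first measures against those surviving to the earliest entry day. The two sets of figures are therefore not interchangeable. With lags drawn from an exponential distribution with a mean of 30 days, ordinary Kaplan-Meier gave 28.2% and 61.0%, while delayed entry gave 22.7% and 55.3%, close to the true 22.8% and 55.2%.

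**Is the treatment-initiation curve clean?** Not necessarily. Section 9.2 requires entry into MSB-GVHD002, and Section 6.3 allows consent as late as Day 180 (±7 days). A child consenting at Day c cannot have died before Day c. As an extreme case, if all consented at Day 100, the curve from infusion would read S^(80/180): 79.7%, 85.3% and 90.6% for true values of 60%, 70% and 80%. Children who consented together with MSB-GVHD001 add no such bias.

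**The case against.** The strongest reply is that the planned Day 180 results already use the right origin. Study day counts from first infusion, the disposition table runs from Day 0 to Day 180, and Section 9.5.1 starts at first treatment. This stands. A reader might infer that the Day 180 survival result, a primary safety parameter, is itself inflated by the early origins. The documents do not support that: counts of children alive or dead at Day 180, and the Section 9.5.1 tests and curves, do not depend on them.

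Second, Section 9.4.2 defines times and names no curve for the early origins; Kaplan-Meier comes from the general sentence in Section 9.1, qualified as appropriate, and a detailed SAP was still to be finalised. This is fair in part. The SAP could correct the rule, but nothing visible says that it will. Event and censoring times from those origins, analysed by the only method named, give the biased estimate.

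Third, a reader might infer that these curves would be set against the 5% to 30% one-year survival in Sections 1.2 and 2.1, to the product's advantage. No section plans that comparison. The figures are background, and they refer to one year, whereas evaluation here ends at Day 180. Section 1.3 mentions historical controls only as a reason for choosing the grading scale.

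Fourth, the sizes rest on assumptions. That is correct; only the direction is secure.

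**Conclusion.** The concern holds for the two early origins only. With infusion required for entry, no delayed entry specified, and any positive lag and hazard, ordinary Kaplan-Meier from transplant or aGVHD onset is biased upward as an estimate of survival from those dates. This is a rule to change, not merely a missing detail.

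The illustrative excess for the transplant origin is roughly 2 to 4 points with lags of 20 to 60 days and 5 to 10 points with lags of 30 to 120 days. It rests on a constant hazard, 60% to 80% survival at 180 days from infusion, and uniform lags, none of which the documents give. For the onset origin only the fixed-lag illustration is available.

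It would also go too far to treat the treatment-initiation curve as free of the problem. Where the analysis set requires entry into MSB-GVHD002, late consent can create guaranteed survival time there too. How much depends on consent dates that the documents do not report.

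**What to change.** In Section 9.4.2 and the SAP:

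- Use first infusion as the origin for Day 180 survival estimates.
- If transplant- and onset-origin curves are kept, enter each child into the risk set at first infusion (left truncation). Use the MSB-GVHD002 consent date instead where the analysis set requires entry into that study and consent came later.
- Apply the same late-consent entry rule to the treatment-initiation curve.
- Show numbers at risk, and label the curves as conditional on survival to entry.

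The cost is a few sentences and an entry-date variable. The infusion date is already needed for study day, the transplant and onset dates for Section 9.4.2, and the consent date is on record. The downside is that the curves become less favourable and are imprecise early on, when few children are at risk. Delayed entry cannot recover survival before the earliest entry day, which is why the label is needed.

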### **9.4.3 Ectopic Tissue Formation**

To detect potential ectopic tissue formation, a radiologist and an Investigator at each study site may compare the CT scan or MRI performed during screening with the CT scan or MRI those performed at study end, if available, to determine if there is ectopic tissue formation. The same method of radiologic scan should be used for both evaluations. If formation of ectopic tissue is suspected, further evaluation may include MRI or positron-emission tomography (PET) scanning, and possibly biopsy.

As noted above, (S)AEs which represent ectopic tissue foci will be summarized by numbers and percentages.

### **9.4.4 Other**

For each applicable time point, key laboratory data, vital signs and safety laboratory parameters will be tabulated. Vital signs and laboratory parameters will be assessed for clinically significant abnormalities and shifts from baseline (baseline as obtained in protocol MSB-GVHD001) will be presented.

## **9.5 Secondary Endpoints Analysis**

### **9.5.1 Assessment of Survival at Day 180**

Survival will be assessed from initial remestemcel-L treatment to the end of study/Day 180. The numbers with percentages for survival, non-survival, or missing, including lost to follow-up, will be summarized at Day 180. For tabulating responders at Day 28 from the MSB-GVHD001 study versus survivors at Day 180 the present study, percentages of survivors and deaths will be based on all subjects, including those with missing survival information for the lost to follow-up or withdrawn subjects. The association between Day 28 OR and survival at Day 180, and between Day 28 VGPR and survival at Day 180, will be tested for statistical significance. First, the associations will be tested using a Cochran–Mantel–Haenszel (CMH) test, stratifying by baseline aGVHD grade. Day 180 survival Kaplan-Meier curves will be plotted by Day 28 responder and non-responder groups, and differences between these groups will be tested for any statistically significant difference using the log-rank test. The odds ratio for survival at Day 180, given responder status at Day 28, will be presented and tested for statistical significance (whether statistically significantly greater than 1).

[REDACTED]

[REDACTED]

[REDACTED]

[REDACTED]

[REDACTED]

[REDACTED]

[REDACTED]

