### 1.3 Grading of Acute GVHD

Acute GVHD is a heterogeneous set of disease processes that potentially involves multiple organ systems, with varying degrees of severity by organ system. Disease onset typically manifests most commonly in the skin, with the GI tract and liver as the next most common sites involved. Historically, classification systems of aGVHD have been established to segregate aGVHD according to severity. The severity grade of aGVHD has been shown to correspond to overall survival, with increased transplant-related mortality correlating with higher aGVHD grade.

One of the first grading systems, published by Glucksberg and colleagues in 1974, involves assigning a stage of 1 to 4 to each involved organ, as described in Table 2, and combining these stages to yield an overall grade ranging from I to IV (Table 3).

Another grading system, which was devised by the International Bone Marrow Transplant Registry (IBMTR) and used in Protocol MSB-GVHD001, classifies aGVHD severity on a scale of A to D. The selection of the IBMTR was based on the use of this scale in previous programs and studies with remestemcel-L, thereby allowing for use of historical controls from those studies. Table 3 presents a summary of the IBMTR grading systems for aGVHD based on stages of organ severity.

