#### 1.4 Clinical Endpoints for Evaluation of aGVHD Treatment

An important step in evaluating new treatment for aGVHD is to establish meaningful clinical endpoints that would enable effective comparison of clinical benefit between different treatment agents. Until more recently, no formal guidance or recommendations existed regarding the appropriate clinical endpoints for assessing aGVHD treatment.

As with other diseases with grave prognosis, the risk of death associated with aGVHD is considerable. Thus, endpoints for aGVHD trials that indicate clinical benefit would, appropriately, be those related to improvements in survival.

Response to treatment at fixed time points after initiating treatment, including complete response (CR), overall response (OR), partial response (PR) and very good partial response (VGPR), as defined in Table 4, have been shown in several studies to be associated with improvement in mortality up to 2 years post-transplant. In particular, OR, as defined in Table 4, to treatment at Day 28 was associated with improved non-relapse mortality at 6 months and 2 years and has been supported by a number of different studies as a surrogate endpoint for transplant-related mortality.

VGPR, which describes a state of near CR, with a few qualifiers, as described in Table 4, was an endpoint that was also recommended by an expert panel of the American Society for Blood and Marrow Transplant (ASBMT) in 2009 in response to the consensus that CR was too stringent an endpoint, while PR was an inadequate measure of response. This is also an endpoint of interest

to regulators, as endpoints in the field are evolving; by capturing this endpoint MSB will span the whole of the response endpoints currently considered.

Consequently, OR and VGPR will be the endpoints used to evaluate treatment effect in Protocol MSB-GVHD001.

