## 2. CLINICAL RATIONALE

### 2.1 Rationale for the Study

There are currently no approved therapies for aGVHD in the US. Standard front-line treatment generally consists of corticosteroid, which produce a complete response in about half of all subjects. Even with the availability of corticosteroids, approximately 10% to 30% of aGVHD subjects develop more severe aGVHD of Glucksberg Grades III or IV. A variety of immunosuppressants are currently used as second-line therapy, though none of these have established efficacy against steroid-refractory aGVHD. The reported one-year survival rate for subjects that do not respond to steroid therapy ranges from 5% to 30%. There is thus a strong need for agents with demonstrated efficacy for treating steroid-refractory aGVHD.

MSB-GVHD001 will provide a series of prescribed doses of remestemcel-L and a follow up period of 100 days. There is a great interest in collecting data regarding treatment of aGVHD with respect to the duration of response, the ability to taper steroid and other secondary treatment and thereby mitigate potential side effects, the development of chronic GVHD after at least partial response to treatment, and any change in quality of life. Accordingly, this study will assess the efficacy and safety of remestemcel-L in pediatric patients with aGVHD refractory to corticosteroid.

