#### 4.1.1 Primary Endpoints

To describe the safety through 180 days of remestemcel-L treatment in subjects who participated in Protocol MSB-GVHD001 and received at least one infusion of remestemcel-L.

Safety parameters to be assessed include:

1. Adverse events
2. Serious adverse events
3. Survival through Day 180
4. Ectopic tissue formation.

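### Section 2.1 states an efficacy aim that the readable analysis plan cannot serve: the tests in Section 9.5.1 ask whether Day 28 response predicts Day 180 survival, not whether remestemcel-L works

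*Combined protocol and SAP*

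**What the plan says.** Section 2.1 ends: "Accordingly, this study will assess the efficacy and safety of remestemcel-L in pediatric patients with aGVHD refractory to corticosteroid". The operative sections are narrower. The primary endpoint in Section 4.1.1 is "To describe the safety through 180 days of remestemcel-L treatment in subjects who participated" in MSB-GVHD001. Sections 3.1 and 4.1 add only an exploration of how long responses last, and Section 3.2 is about safety alone.

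There is no untreated group. Section 5.2.1 requires: "Subjects must have participated in Protocol MSB-GVHD001 and have received at least one infusion of remestemcel-L". Historical controls appear in Section 1.3, where the IBMTR scale is chosen for MSB-GVHD001, "thereby allowing for use of historical controls from those studies". The readable part of Section 9 specifies no comparison with them.

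Section 9.5.1 holds the only significance tests in the readable text: "The association between Day 28 OR and survival at Day 180, and between Day 28 VGPR and survival at Day 180, will be tested" for significance. The methods are a CMH test "stratifying by baseline aGVHD grade", a log-rank test between Day 28 responders and non-responders, and an odds ratio for survival given response, tested for being above 1.

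For all subjects together, Section 9.5.1 plans counts and percentages alive, dead or missing at Day 180. The only survival curves it specifies are split by responder status. Section 9.1 allows Kaplan-Meier curves where appropriate and adds: "Confidence intervals, if presented, will have a two-sided 95% confidence level".

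**The concern.** A study that declares an efficacy aim should contain an analysis whose result depends on whether the drug works. Here the readable tests take two inputs, Day 28 response and Day 180 survival, both measured in treated children only. Children with a better outlook may both respond more often and survive longer, so responders can outlive non-responders on an inert product.

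The risk is one of interpretation. If the report carries the Section 2.1 aim and its only visible p-values come from the responder comparison, a reader may take a significant result as evidence that remestemcel-L improved survival. Day 180 survival in everyone treated, the more informative quantity, has no interval guaranteed.

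**Working it through.** **1. No figure to reproduce.** The documents give no sample size, power, test alpha, response rate or survival by response. Numbers below marked as assumed are not in the protocol.

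**2. What each test uses.**
- CMH: Day 28 response (OR, then VGPR) against Day 180 survival, within baseline grade.
- Log-rank: survival curves by responder status.
- Odds ratio: odds of survival given response, tested above 1.

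None contains a treatment contrast, and none can, because all subjects were treated.

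**3. Why the result does not track drug effect.** Write r for the response rate, S_R for survival in responders and S_N for survival in non-responders. Then

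- overall survival = r·S_R + (1 − r)·S_N
- odds ratio = [S_R/(1 − S_R)] / [S_N/(1 − S_N)]

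The odds ratio does not contain r. Assume S_R = 80% and S_N = 40%:

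- odds ratio = (0.8/0.2)/(0.4/0.6) = 6
- at r = 50%, overall survival = 0.5×0.8 + 0.5×0.4 = 60%
- at r = 70%, overall survival = 0.7×0.8 + 0.3×0.4 = 68%

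A drug that moved r from 50% to 70% with S_R and S_N unchanged would raise survival by 8 points and leave the odds ratio at 6. An inert drug in a population where response merely marks a better prognosis would give the same odds ratio.

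**4. Expected direction.** Section 1.4 says the response categories "have been shown in several studies to be associated with improvement in mortality up to 2 years post-transplant". It reports lower non-relapse mortality at 6 months and 2 years after Day 28 overall response. Section 2.2 says response by Day 28 goes with Day 100 survival. These statements concern aGVHD treatment in general, so a positive direction is expected on the protocol's own account.

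**5. How likely is significance?** Two-proportion power at two-sided 5%, n per group, p̄ = (p1 + p2)/2:

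power = Φ{ [|p1 − p2| − 1.96·√(2p̄(1 − p̄)/n)] / √([p1(1 − p1) + p2(1 − p2)]/n) }

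Example, 80% vs 40%, n = 30: (0.40 − 1.96×0.1265)/0.1155 = 1.32, so power is 91%.

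| Assumed survival, responders vs non-responders | n = 15 | n = 30 | n = 50 |
|---|---|---|---|
| 60% vs 45% | 12.5% | 21% | 32% |
| 70% vs 40% | 37% | 65% | 87% |
| 80% vs 40% | 62% | 91% | 99% |

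These are power figures against an association assumed to be real. They are not false-positive rates of the planned tests.

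**6. Does a Day 28 landmark change this?** Simulation with no drug effect, 3,000 trials per setting. Assumed: N = 30 to 100; baseline Day 180 survival 40% or 60%; about half responding; an unmeasured prognostic factor shifting log-hazard and log-odds of response by 0.5 or 1.0 per SD. A log-rank test restricted to subjects alive at Day 28 found responders living significantly longer (z > 1.96) in 6% to 49% of trials. A landmark removes the early-death artefact, but the question remains prognostic.

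**The case against.** The strongest reply is that Section 9.5.1 does what it says. It calls these tests of association, and no readable section presents them as evidence of drug effect. Section 1.4 treats Day 28 response as a surrogate supported by other studies, so checking it against Day 180 survival in this population is a coherent secondary analysis. Section 1.4 also assigns evaluation of treatment effect to MSB-GVHD001. The efficacy sentence in Section 2.1 follows a list covering duration of response, steroid taper, chronic GVHD and quality of life, not the responder tests. All of this stands, and it limits the fault to a mismatch between one sentence and what the design can show.

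Three stronger readings are tempting and are not supported:

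- A reader might infer that the sponsor plans to cite the responder p-value as proof of efficacy. No passage says so.
- A reader might infer that the tests have an inflated type I error. Under the hypothesis they state, no association, rejecting when response is truly prognostic is correct.
- A reader might infer that these are the study's only p-values. That cannot be verified: the contents list Sections 9.5.2 to 9.5.6 and further redacted entries whose text is not readable, and Section 9.1 defers to a detailed SAP.

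It is also fair to say that an uncontrolled Kaplan-Meier estimate cannot separate an active drug from an inert one. The estimate is recommended for description only.

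**Conclusion.** The point holds as a conflict between a stated aim and the readable analysis. Section 2.1 promises an efficacy assessment. Sections 3.1, 3.2, 4.1 and 4.1.1 describe safety follow-up with exploration of duration of response, and the tests in Section 9.5.1 address prognosis. The tests may stay; they cannot carry the efficacy claim.

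The expected direction is firm, resting on Sections 1.4 and 2.2. Significance is not assured: across the assumed gaps and group sizes tabulated, power runs from 12.5% to 99%, and the documents do not say where this study lies. The conclusion is confined to readable text. It deserves correction because it sets what the study may conclude and costs little to repair.

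**What to change.** 1. **Section 2.1.** Replace the claim to assess efficacy and safety with a statement that the study will describe safety and explore duration of response, matching Sections 3.1 and 4.1.
2. **Section 9.5.1.** Add a sentence such as: *The CMH, log-rank and odds-ratio tests evaluate Day 28 response as a predictor of Day 180 survival; they will not be used to draw conclusions about the efficacy of remestemcel-L.*
3. **Section 9.5.1.** Require a descriptive Kaplan-Meier estimate of Day 180 survival from first infusion, with a two-sided 95% confidence interval, in all MSB-GVHD001 subjects who received at least one infusion. Include those who never entered MSB-GVHD002, with deaths counted and survivors censored at last contact as in Section 9.4.2. This matters because Section 6.3 allows consent up to Day 180, so a set limited to entrants favours children who lived long enough to consent.
4. **Populations.** Report this estimate alongside secondary endpoint 1, which Section 4.1.2 limits to subjects who completed initial therapy. Reconcile the safety population in the synopsis (all treated in MSB-GVHD001) with Section 9.2 (treated and entered into MSB-GVHD002).

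The cost is a few sentences and one estimate with its interval; Section 9.1 already plans survival data across both studies. No visit or procedure changes. The downside is that the responder-survival p-value can no longer be cited as efficacy evidence. Censoring non-entrants also assumes that their later survival resembles that of subjects still followed, which the report should state.
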